4.3 Criteria for Delay of Vaccination

After enrollment, subjects may encounter clinical circumstances that warrant a delay in subsequent study vaccination. These situations are listed below. In the event that a subject meets a criterion for delay of vaccination, the subject may receive study vaccination once the window for delay has passed as long as the subject is otherwise eligible for study participation.

- Acute moderate or severe infection with or without fever within 3 days of intended study vaccination.
- Fever is defined as body temperature ≥38.0° C within 3 days of intended study vaccination.
- Administration of any vaccine not foreseen by the study protocol within 14 days prior to first vaccination and, if applicable, 7 days prior to the second study vaccination.

Prior to receipt of repeat study vaccination, subjects must be evaluated to confirm that they are eligible for subsequent vaccination. If subjects meet any of the criteria listed below, they should not receive additional vaccinations:

- Subjects who experienced any immediate allergic reaction after the previous study vaccination.
- Subjects who experience any serious adverse event judged to be possibly or probably related to study vaccination, including hypersensitivity reactions.
- Subjects who develop any clinically significant medical condition which, in the opinion of the investigator, may pose additional risk to the subject if he/she continues to participate in the study.
- Subjects who are pregnant.

Subjects who meet any of these criteria must not receive further study vaccinations. However, these subjects should be encouraged to continue study participation, as discussed in section 3.7.

There is clinical circumstance that warrants delay of blood collection for immunogenicity assessments in this study. This situation is listed below. In the event that a subject meets a criterion for delay of blood collection, blood collection may proceed once the window for delay has passed.

• Subject has received a dose of systemic antibiotics less than 3 days before the intended blood collection.

Under such circumstances, a subject may be considered eligible for study enrolment after the appropriate window for delay has passed and inclusion/exclusion criteria have been rechecked, and if the subject is confirmed to be eligible.

5. STUDY PROCEDURES

The sections that follow provide an overview of the procedures that are to be followed in enrolling, evaluating, and following subjects who participate in this clinical study. Visits can be either clinic visits or safety follow-up telephone calls, as specified in the Table below and in the Time and Events Table 5 and 6

Table 5-1: Study Procedures

Visit Category	Procedures				
Pre-vaccination Clinic Visit(s)	Section 5.1 describes procedures to be followed prior to study vaccination: informed consent/assent, screening, enrolment, and randomization				
	Note; Randomization / vaccine allocation in IRT must occur immediately before giving vaccine to subject. If pre-vaccination clinic visit does not happen on the same day as vaccine administration, randomization / vaccine allocation in IRT be performed only on the day of vaccination				
Vaccination Clinic Visit(s)	Section 5.2 describes procedures to be followed during each clinic visit involving vaccination: vaccination, post-vaccination procedures, and post-vaccination reminders				
Post-vaccination Visit(s)	Section 5.3 describes follow-up clinic visits and safety follow-up calls				
Unscheduled Visit(s)	Section 5.4 describes possible procedures to be followed at unscheduled clinic visit				
Study Termination Visit	Section 5.5 describes procedures to be followed at the last study visit for a subject (may include early termination visit)				

5.1 Pre-vaccination Clinic Visit(s)

This section describes the procedures that must be performed for each potential subject prior to vaccination, including obtaining informed consent/assent, screening, enrolment and randomization. All procedures listed in sections 5.1.1 and 5.1.2 can be performed up to 7 days prior to enrolment on Day 1.

Procedures listed in sections 5.1.3 and 5.1.4 must be performed on the same day as vaccination.

5.1.1 Informed Consent/Assent

"Informed consent" is the voluntary agreement of an individual or his/her legal guardian(s) to participate in research. Consent must be given with free will of choice, and without undue inducement. The individual must have sufficient knowledge and understanding of the nature of the proposed research, the anticipated risks and potential benefits, and the requirements of the research to be able to make an informed decision.

"Assent" is a term used to express willingness to participate in research by persons who are by definition too young to give informed consent but who are old enough to understand the proposed research in general, its expected risks and possible benefits, and the activities expected of them as subjects. Assent by itself is not sufficient, however. If assent is given, informed consent must still be obtained from the subject's parent(s) or legal guardian(s). Local laws define who constitutes a "child," and such definitions dictate whether or not a person can legally consent to participate in a protocol (Levine 1988).

Informed consent of the parent(s)/legal guardian(s) and assent of subject following local IRB/EC guidance **must** be obtained before conducting any study-specific procedures (i.e., all of the procedures described in the protocol). The process of obtaining informed consent and assent should be documented in the subject source document in addition to maintaining a copy of the signed and dated informed consent. Additional specifics regarding the informed consent and assent processes are located in section 13.2, Informed Consent Procedures.

If a subject or subject's guardian/parent is unable to read, an impartial witness should be present during the entire informed consent and assent discussion. An impartial witness is defined as a person who is independent from trial conduct, who cannot be unfairly influenced by those involved with the trial, who attends the informed consent process if the subject or the subject's legally acceptable representative cannot read, and who reads the informed consent form and any other written information supplied to the subject. After the written informed consent form and any other written information to be provided to subjects, is read and explained to the subject or subject's guardian/parent and after the subject or subject's guardian/parent has verbally consented to the subject's participation in the trial and, if capable of doing so, has signed and personally dated the informed consent form, the witness should sign and personally date the consent form. By signing the consent form, the witness attests that the information in the consent form and any other written information was accurately explained to, and apparently understood by, the subject or subject's guardian/parent and that informed consent was freely given by the subject or subject's guardian/parent.

If at any point in the trial after Day 1, subject has reached the age when the individual informed consent must be given in addition to the provided assent form, the subject's informed consent has to be obtained prior to any study-specific procedures.

5.1.2 Screening

After an individual or individual's parent/guardian has consented to participate in the study and informed consent/assent has been signed, that individual will be given a unique sequential Screening Number by the investigator. The subject's unique Screening Number will be documented in the Screening and Enrolment log. The eligibility of the subject will be determined based on the inclusion and exclusion criteria listed in section 4. , Selection of Study Population and evaluated during this screening procedure.

Prior to study enrolment, demographic data will be collected from the subject, including date of birth, gender, race, and ethnicity.

Medical history will also be collected, including but not limited to any medical history that may be relevant to subject eligibility for study participation such as prior vaccinations, concomitant medications, and previous and ongoing illnesses or injuries. Relevant medical history can also include any medical history that contributes to the understanding of an adverse event that occurs during study participation, if it represents an exacerbation of an underlying disease/pre-existing problem. Medical history will be collected from birth for naive subjects and from end of participation in study V102_15 for follow-on subjects.

Review of systems is a structured interview that queries the subject and/or parent(s)/legal guardian(s) as to any complaints the subject has experienced across each organ system. This will be performed before enrolment and used to guide physical examination.

If applicable, prior and concomitant medications or vaccinations taken prior to start of study should be collected (refer to section 6.5, Prior and Concomitant Medications and Vaccines for further details).

Collect vital signs (heart rate, respiratory rate, blood pressure, and temperature). Measure height and weight.

Perform pregnancy testing in women of childbearing age (refer to section 3.5, for guidance regarding the procedure).

A general physical examination is to be performed by a qualified health care practitioner. "Qualified health care practitioner" refers to any licensed health care professional who is

permitted by institutional policy to perform physical examinations and who is identified within the Study Staff Signature Log.

These data will be written in the source document (see section 9.1 Source Documentation).

In the event that the individual is determined ineligible for study participation, he/she is considered a screen failure. The reason for screen failure must be documented in the Screening and Enrolment log. If the individual is determined to be eligible for the study, he/she will be enrolled into the study.

5.1.3 Enrolment

After the signed informed consent form has been obtained and an individual is determined to be eligible for study participation, the subjects will be enrolled using Interactive Response Technology (IRT) system. For follow-on subjects, the same Subject ID that was assigned in the parent study will be used for the extension trial. For naive subjects, a new Unique Subject ID will be assigned in IRT. The Subject ID number consists of a 7 digit number resulting from the combination of the site number and the subject's order of randomization at the site. Access to IRT can be obtained by the site staff either via web or telephone (as back up).

As soon as the target number (upper limit) of naive subjects in each vaccine (MenABCWY or MenB) group has been reached, the enrollment will be frozen. Additional subjects may be enrolled into the study at the discretion of the sponsor in the case of any subject who was randomized but did not receive any study vaccine.

5.1.4 Randomization

Enrolled naive subjects will be randomized in the IRT system and automatically assigned a unique Subject ID. Enrolled follow-on subjects will be assigned the same Subject ID that was used in the parent trial. The Subject ID assigned by IRT will be the subject's unique identification number for all eCRFs and associated study documentation that will be used for duration of the study. After randomization, the Screening Number ceases to be used and remains in the Screening and Enrolment Log only. The list of randomization assignments is produced by the IRT service provider and approved by GSK Randomization Office according to applicable GSK Standard Operating Procedure (SOP).

If for any reason, after signing the informed consent form (ICF), the subject who is eligible and enrolled fails to be randomized, this is called a randomization failure and the early termination study procedures must be applied. The reason for all randomization failures should be recorded in the Screening and Enrolment Log and in the source

document as specified in the Source Data Agreement (SDA). The information on subjects who are randomization failures should be kept distinct from subjects who are screen failures, as described in section 5.1.2, Screening.

If for any reason, after randomization the subject fails to undergo treatment, this is an Early Termination and the reason should be recorded in source document as specified in the SDA. The information on these Early Termination subjects should be kept distinct in the source documentation from randomization failures.

For follow on subjects, on Visit **D**ay 1, IRT will assign a pack ID of the same treatment received in the V102 15 (MenABCWY or rMenB+OMV).

For Naive subjects, IRT will randomly assign 1 dose of MenABCWY or rMenB+OMV, based on a 1:1 ratio. IRT will automatically schedule a second visit on Day 61 for naive subjects to receive a second dose of the same vaccine received on **D**ay 1.

(Amended 4 April 2018)

5.2 Vaccination Clinic Visit(s)

The first vaccination will be performed on **D**ay 1 for all subjects. The naive subjects will receive their second dose at Day 61 visit.

For studies which have visits for concomitant vaccinations or treatments, see section 6.5, Prior and Concomitant Medications and Vaccines for those visit procedures.

Ensure all serology samples are taken prior to each vaccination, if applicable. Refer to section 3.5 for further detail regarding the sample volume and general handling of blood sample.

After completing the pre-vaccination procedures on **D**ay 1 for all subjects and at Day 61 for naive subjects, administer the vaccine to the subject according to the procedures described in section 6.3. Vaccine Preparation and Administration.

Prior to administration of each vaccination at visit Month 1, Month 2, Month 6 and Month 12, confirm that the subject is eligible for additional study vaccination and does not meet any criteria for delaying additional study vaccinations as described in section 4., Selection of Study Population.

Pre-vaccination procedures at Visits Day 1 for all subjects and at Day 61 for the naive subjects, Month 2, Month 6 and Month 12

- A general physical examination is to be performed by a qualified health care practitioner. "Qualified health care practitioner" refers to any licensed health care professional who is permitted by institutional policy to perform physical examinations and who is identified within the Study Staff Signature Log.
- Perform pregnancy test in all female subjects of childbearing potential (refer to section 3.5 for guidance regarding the procedure).
- Ensure all serology samples are taken **prior** to each vaccination, as applicable (all subjects at Day 1).
- Use IRT system to assign a Pack Number containing the treatment to be administered to the naive and follow on subjects. IRT will assign a treatment according to a randomization list to naive subjects. IRT will assign to follow on subjects the vaccination (MenABCWY or MenB) they received in the V102_15 study. Each Pack Number, actually administered to the subject, must be recorded in the eCRF.

After completing the pre-vaccination procedures at Visit Day 1 and Day 61 for the naive subjects, administer the vaccine to the subject according to the procedures described in section 6.3, Vaccine Preparation and Administration.

(Amended 4 April 2018)

5.2.1 Post-vaccination Procedures

The following post-vaccination procedures will be performed on **D**ay 1 for all subjects and at **D**ay 61 for the naive.

After vaccination, the subject will be observed for at least 30 minutes including observation for unsolicited adverse events, solicited adverse events, and body temperature measurement. Record all safety data collected during this time in the subject's source document.

A Subject eDiary will be used in this study to document solicited adverse events. The Subject eDiary is the only source for collection of these data; therefore, it is critical that the subject completes the Subject eDiary correctly. The subject should be trained on how and when to complete each field of the Subject eDiary.

The subject or parent(s)/legal guardian(s) should be trained on how to self-measure local solicited adverse events and body temperature. The measurement of solicited local adverse events is to be performed using the ruler provided by the site.

The subject or parent(s)/legal guardian(s) should be instructed how to perform body temperature measurement using the thermometer provided by the site. If the subject feels

unusually hot or cold during the day, the subject or parent(s)/legal guardian(s) should check body temperature. If the subject has fever, the highest body temperature observed that day should be recorded in the Subject eDiary.

Subject Diary training should be directed at the individual(s) who will perform the measurements of adverse events and who will enter the information into the Subject Diary. This individual may not be the subject or parent(s)/legal guardian(s), but if a person other than the subject or parent(s)/legal guardian(s) enters information into the Subject eDiary, this person's identity must be documented in the subject's source record]. Any individual that makes entries into the Subject eDiary must receive training on completion of the Subject eDiary at the time of the visit. This training must be documented in the subject's source record.

The same individual should complete the Subject eDiary throughout the course of the study.

Subject eDiary assignment and use:

- Each subject or parent(s)/legal guardian(s) will be assigned a Subject eDiary and shown how to use the device this will include how to access the diary, performing test data entry on sample questions, and how to charge and store the device.
- The subject or parent(s)/legal guardian(s)] will self-select a numeric access code secret to themselves. The same individual should make the assessments and complete the Subject eDiary throughout the course of the study.
- The subject and/or parent(s)/legal guardian(s) will select an alarm time that suits their daily routines whilst ensuring compliance with protocol requirements.

Subject eDiary instructions must ensure that the subject or parent(s)/legal guardian(s) understands the following:

- Timely completion of the Subject eDiary on a daily basis is a critical component to study participation.
- The Subject eDiary will allow certain time windows for completion of each day's observations.
- The Subject eDiary employs the use of audio-visual alarms to ensure timely completion of data entry.
- The trained and assigned user of the Subject eDiary must not share access codes with anyone.

- A helpdesk will be provisioned for them in case of technical issues, though it must be stressed that the Helpdesk is not a replacement for normal medical care and no medical issues can be discussed with the agents.
- The Subject eDiary itself must never be considered a substitute for direct medical care and any concerns must be communicated to site staff as soon as possible.

The site should schedule the next study activity clinic visit or safety follow-up call with the subject or parent(s)/legal guardian(s).

The subject and/or parent(s)/legal guardian(s) should be reminded of the next planned study activity. The subject and/or parent(s)/legal guardian(s) will be reminded to complete the Subject eDiary and to contact the site if there are any questions, and to contact the site immediately (or as soon as the subject is medically stable) if the subject has a medical condition that leads to a hospitalization or an emergency room visit or to a visit to/by a doctor or is of concern.

(Amended 4 April 2018)

5.2.2 Post-vaccination Reminders

No post-vaccination reminder calls will be performed in the study.

The subject or parent(s)/legal guardian(s) will receive daily reminders via the Subject eDiary device's in-built audio-visual alarms to alert the user to complete the diary during the post vaccination period. From Day 1 though Day 87, or until resolution of the last reported solicited AE, the users will receive daily alerts through the Subject eDiary to record the incidence of any potential unsolicited AEs, and whether these AEs were medically attended (defined as symptoms or illnesses requiring hospitalization, or emergency room visit, or visit to/by a health care provider), or were of concern. In case of such events, subjects/parents will be instructed to contact the site as soon as possible to report the event(s).

The Subject eDiary system will also allow for regular alerts to be issued via email to site staff indicating where subjects may need to be contacted due to:

- Non-compliance (i.e. failing to enter or transmit diary data),
- Reporting of any severe solicited reactions,
- Subject experienced an unsolicited adverse event that was medically attended or was
 of concern.

Sites must assess these alerts when received and contact subjects as necessary. Please refer to section 3.8, Premature Withdrawal from Study and section 7.1.3, Evaluation of Adverse Events for guidance on necessary action in the event of one of these alerts.

Unsolicited Adverse Event Safety Follow Up Calls

The site will call the subjects or parent(s)/legal guardian(s) 15 days after the vaccination to collect/observe any safety concerns (unsolicited AEs, SAEs, and medically attended AEs).

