	Visit Window (Days)	-5 to 1	~24 months after last meningococc al vaccination (-1/+3 months)	-1 to +3	-2/+2	-7 to +10	-14 to +14	-14 to +14
	Visit Interval			5 days after visit 1		30 days after visit 1		
	Visit Number	Pre- vaccination	1	2		3		
Study Event	References							
Pregnancy Test	Sections 3.5 and 5.1.2	X	X b,d					
Exclusion/Inclusion Criteria	Section 4.	X	X ^d					
Randomization/Pack number allocation	Section 5.1.4		X ^b					
30 Minutes Post Injection Assessment	Section 5.2.1		X					
Subject eDiary Dispensed with Training	Section 5.2.1		X					

Confidential

Visit Type	Screening	Clinic Visit	Clinic Visit	Phone Call	Clinic Visit	Phone Call	Phone Call
Study Day		1	6	16	31	91	181
Visit Window (Days)	-5 to 1	~24 months after last meningococc al vaccination (-1/+3 months)	-1 to +3	-2/+2	-7 to +10	-14 to +14	-14 to +14
Visit Interval			5 days after visit 1		30 days after visit 1		
Visit Number	Pre- vaccination	1	2		3		
References							
Section 5.3.1					X		
Section 7.1		X		X	X	X	X
Section 7.1.4		X		X	X	X	X
Sections 7.1.4.1 and 7.1.3		X		X	X	X	X
Sections 5.1.2 and 6.5	X	X^d		X	X	X	X
	Visit Window (Days) Visit Interval Visit Number References Section 5.3.1 Section 7.1.4 Sections 7.1.4.1 and 7.1.3 Sections 5.1.2	Study Day Visit Window (Days) Visit Interval Visit Number References Section 5.3.1 Section 7.1.4 Sections 7.1.4.1 and 7.1.3 Sections 5.1.2	Study Day 1 -24 months after last meningococc all vaccination (-1/+3 months)	Visit Type Screening Clinic Visit Visit	Study Day 1 6 16	Study Day 1 6 16 31	Study Day 1 6 16 31 91

	Visit Type	Screening	Clinic Visit	Clinic Visit	Phone Call	Clinic Visit	Phone Call	Phone Call				
	Study Day		1	6	16	31	91	181				
	Visit Window (Days)	-5 to 1	~24 months after last meningococc al vaccination (-1/+3 months)	-1 to +3	-2/+2	-7 to +10	-14 to +14	-14 to +14				
	Visit Interval			5 days after visit 1		30 days after visit 1						
	Visit Number	Pre- vaccination	1	2		3						
Study Event	References							_				
Serology blood draw	Section 3.5		X ^a	X		X						
Study Termination												
Termination Procedures	Section 5.5							X ^e				

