Subject eDiary Reviewed and Collected	Section 5.3.1				X				X		
Assess all AEs	Section 7.1		X	X	X	X		X	X	X	X
Assess SAEs	Section 7.1.4		X	X	X	X		X	X	X	X
Assess for medically attended AEs, AEs leading to withdrawal	Sections 7.1.4.1 and 7.1.3		X	X	X	X		X	X	X	X
Assess relevant medications	Sections 5.1.2 and 6.5	X	X	X	X	X		X	X	X	X
Immunogenicity											

	Visit Type	Screening	Clinic Visit	Phone Call	Clinic Visit	Clinic Visit	Clinic Visit	Phone Call	Clinic Visit	Phone Call	Phone Call
	Study Day		1	16	31	61	66	76	91	151	241
	Visit Window (Days)	-5 to 1	n/a	-2/+2	-7 to +10	-7 to +10	-1 to +3	-2/+2	-7 to +10	-14 to +14	-14 to +14
	Visit Interval				30 days after visit 1		5 days after visit 3		30 days after visit 3		
	Visit Number	Pre- vaccinatio n	1		2	3	4		5		
Study Event	References										
Serology blood draw	Section 3.5		X a		X		X		X		
Termination Procedures	Section 5.5										X^{f}
Notes: a Confirm consent form(s) signed prior to any procedures. b Procedure to be performed prior to vaccination c Symptom-directed physical examination d Some procedures may not need to be repeated if screening is performed before Day 1. Inclusion/exclusion criteria should, however, be rechecked prior to vaccination even if performed before. Subjects who terminate early are recommended to complete certain study procedures. See section 5.5.1 for details.											

LIST OF ABBREVIATIONS

AE Adverse Event
ANOVA Analysis of Variance
CDM Clinical Data Management
CI Confidence Interval

CI Confidence Interval
CRM Cross Reactive material

CRO Contract Research Organization

EC Ethics Committee

eCRF Electronic Case Report Form
EDC Electronic Data Capture
EDT Electronic Data Transfer
EMA European Medicines Agency

FAS Full Analysis Set

FDA Food and Drug Administration
fHbp Factor H Binding Protein
GCP Good Clinical Practices
GMT Geometric Mean Titer
GMR Geometric Mean Ratio

hSBA Human Serum Bactericidal Assay

HT-hSBA High-Throughput Human Serum Bactericidal Assay

IB Investigator's Brochure ICF Informed Consent Form

ICH International Conference on Harmonization of Technical

Requirements for Registration of Pharmaceuticals for Human Use

IM Intramuscular

IRB Institutional Review Board IRT Interactive Response Technology

LSLV Last Subject Last Visit LLOQ Lower Limit of Quantitation

MedDRA Medical Dictionary for Regulatory Activities

NadA Neisserial Adhesin A

NHBA Neisseria Heparin Binding Antigen

PorA Porin A

PPS Per Protocol Set
PT Preferred Term
RR Relative Risk

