8.1.2.3 Secondary Safety Endpoint(s)

Safety of the study vaccines will be assessed in all subjects in terms of the percentages of subjects with reported adverse events including:

- Any solicited and unsolicited AEs reported within 30 minutes after vaccination at Day 1 (for all subjects) and also Day 61 (for naive subjects only);
- Solicited local and systemic AEs reported from Day 1 (6 hours) to Day 7 after vaccination at Day 1 (for all subjects) and Day 61 *to Day* 67 (for naive subjects);
- Other indicators of reactogenicity (e.g. use of analgesics / antipyretics, body temperature) within 7 days after vaccination at Day 1 (for all subjects) and Day 61 (for naive subjects);
- Unsolicited AEs reported from Day 1 to Day 31 for all subjects and Day 61 to Day 91 for naive subjects;

_

¹ Serogroup B test strains to be used in the study: M14459 (fHbp), 96217 (NadA), NZ98/254 (PorA) and M07-0241084 (NHBA).

² For subjects with prevaccination hSBA titers \leq LLOQ, a post-vaccination hSBA \geq 4 times the LLOQ; for subjects with prevaccination hSBA titers \geq LLOQ, an increase of at least 4 times the prevaccination hSBA.

- Medically-attended AEs reported during the entire study period (up to **D**ay 181 for follow-on subjects and up to Day 241 for naive subjects);
- AEs leading to premature withdrawal from the study during the entire study period (up to **D**ay 181 for follow-on subjects and up to Day 241 for naive subjects);
- SAEs reported during the entire study period (up to **D**ay 181 for follow-on subjects and up to Day 241 for naive subjects).

(Amended 4 April 2018)

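### The Day 1 to 87 eDiary alert period in Protocol 5.2.2 matches no dose, visit or AE window and cannot run alongside the device schedule in Tables 5 and 6

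*Protocol*

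**What the plan says.** Protocol 5.2.2 (Post-vaccination Reminders) states: "From Day 1 though Day 87, or until resolution of the last reported solicited AE, the users will receive daily alerts". The alerts ask users "to record the incidence of any potential unsolicited AEs, and whether these AEs were medically attended". Subjects who have such an event are told to contact the site. The system also e-mails the site when an unsolicited event is medically attended or of concern, and the site must assess that alert. Nothing in the section varies the period by group or by dose.

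Other sections fix the timing that the alerts should fit:

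- **Doses.** Follow-on subjects have one dose, on Day 1. For the others, Protocol 5.2 says: "The naive subjects will receive their second dose at Day 61 visit". Table 6 allows that visit from 7 days early to 10 days late.
- **Endpoint windows.** Protocol 8.1.2.3 lists "Unsolicited AEs reported from Day 1 to Day 31 for all subjects and Day 61 to Day 91 for naive subjects", and separately "Medically-attended AEs reported during the entire study period" (to Day 181 in follow-on subjects, Day 241 in naive subjects).
- **Device issue.** The row "Subject eDiary Dispensed with Training" is marked at Day 1 in Table 5 (follow-on), and at Days 1 and 61 in Table 6 (naive).
- **Device return.** The row "Subject eDiary Reviewed and Collected" is marked at Days 31 and 91 in Table 6. The corresponding row in Table 5, identified by its reference to "Section 5.3.1", is marked at Day 31 only.
- **Solicited events.** Protocol 3.4.2.1 runs the diary to Day 7 after vaccination, or to resolution if an event is still ongoing.

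**The concern.** An alert period for post-vaccination events should follow the vaccination. This one is a single run of days for everyone, although naive subjects have a second dose 60 days after the first. Taken at face value, the prompts end inside the naive dose-2 window, while the windows after the booster and after the first naive dose are covered in full. Secondary safety objective 3 (Protocol 2.2.2) concerns both naive doses, so prompting that differs between them could contribute to a difference in reported unsolicited events.

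There is also a practical problem. The sentence is an instruction for programming an alarm that triggers site contacts. If the device has been handed back, the alarm cannot reach the subject for much of the stated period. Whoever configures the eDiary must then choose between 5.2.2 and the visit tables without guidance.

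**Working it through.** This is day arithmetic, counting days inclusively. Day 87 is taken as the end of the alerts. The sentence does not say whether its clause on resolution of solicited AEs shortens or lengthens the period.

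**1. Can Day 87 be reproduced?** Adding the protocol's intervals of 5, 6, 7, 15, 30, 90 and 180 days to each nominal dose day gives:

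- from Day 1: Days 6, 7, 8, 16, 31, 91, 181
- from Day 61: Days 66, 67, 68, 76, 91, 151, 241

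None is Day 87, so the figure cannot be derived from the schedule.

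**2. Coverage of the naive dose-2 window, read as study days.** With dose 2 on Day d, the 30-day window runs from d to d + 30 (31 days). Prompted days = min(31, 87 − d + 1).

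| Dose 2 on | Window ends | Prompted days | Unprompted days |
|---|---|---|---|
| Day 54 (earliest allowed) | Day 84 | 31 of 31 | 0 |
| Day 57 | Day 87 | 31 of 31 | 0 |
| Day 61 (nominal) | Day 91 | 27 of 31 (87%) | 4 |
| Day 71 (latest allowed) | Day 101 | 17 of 31 (55%) | 14 |

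Coverage is complete when d + 30 ≤ 87, that is, d ≤ 57. The windows after the booster and after the first naive dose (Days 1 to 31) are covered in full.

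**3. Device in hand, nominal visits.**

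- Follow-on: issued Day 1, collected Day 31. Days 32 to 87 have no device: 87 − 31 = 56 of the 87 days. If the Day 31 visit falls on Day 24 or Day 41 (its window limits), the count is 87 − 24 = 63 or 87 − 41 = 46.
- Naive: collected Day 31, reissued Day 61, collected Day 91. Days 32 to 60 have no device: 60 − 31 = 29 days. Days 61 to 87 do have one.

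**4. Prompted days per dose on each reading.**

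| Reading | Follow-on booster | Naive dose 1 | Naive dose 2 |
|---|---|---|---|
| 5.2.2 alone | 87 | 60 | 27 |
| 5.2.2 limited to days with the device | 31 | 31 | 27 |

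On 5.2.2 alone, both groups have 87 prompted days in total (60 + 27 = 87). With the device limit, follow-on subjects have 31 and naive subjects 31 + 27 = 58.

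**5. If the days are counted from each dose instead.** The dose-2 shortfall disappears, but Day 87 after a Day 61 dose is study Day 60 + 87 = 147. That is 147 − 91 = 56 days after the device is collected. The conflict with the tables remains.

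**The case against.** The strongest reply is that the prompts are not the collection instrument. Protocol 3.1 collects unsolicited AEs by a call 15 days after each dose and a visit 30 days after it. Protocol 5.3.1 and 5.3.2 make those contacts scripted, at the same intervals after each dose, and medically attended AEs are sought at every call and safety visit. At nominal dates the unprompted stretch is Days 88 to 91, and it ends at an interview. This stands, and it is why no material shift in AE percentages should be claimed.

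A second reply is that the sentence does not say study day, sits under a post-vaccination heading, and belongs to a protocol that often counts days from each dose. That is a fair reading, but step 5 shows that it does not remove the device conflict.

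Third, 87 may be a slip for another number. The phrasing resembles the solicited-event rule in 3.4.2.1, and Protocol 5.2 and 7.1 contain other stray timepoints (Months 2, 6, 12 and 13). The documents do not settle this. It is a further reason to correct the sentence.

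Fourth, the text on device return is mixed. Section 5.3.1 speaks of reviewing the diary at the visit and ends with a reminder to complete it, and collection in follow-on subjects rests on the Table 5 row identified by its section reference. Table 6 does state collection, however, and 5.5.1 shows that collecting means taking back the device. The device conflict therefore depends on the tables being followed.

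A reader might infer that follow-on subjects are prompted for far longer than naive subjects, biasing the booster comparison. The documents do not support this. The contrast of 87 with 27 days after the last dose needs alerts on days when the tables say there is no device. With the device limit, the per-dose figures are 31, 31 and 27, and the totals favour naive subjects. The booster and first naive dose windows are fully prompted on both readings.

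**Conclusion.** The point holds as an inconsistency to correct, with a small likely effect. Day 87 corresponds to no nominal visit or AE window. If it is a study day, the prompts fall 4 days short of the nominal naive dose-2 window, with a range of 0 to 14 days across the permitted dose dates. If the device is collected at Day 31 as tabled, 56 of the 87 alert days in follow-on subjects and 29 in naive subjects cannot occur.

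The shortfall figures assume study-day counting and Day 87 as the actual end. The device figures assume nominal visits and collection as tabled. The documents do not show that any AE endpoint would be materially distorted, and the safety objectives carry no hypotheses (Protocol 8.4.3.3.4). The case for acting is that the sentence drives a working alarm and site alerts, and it cannot be carried out as written.

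**What to change.** Reconcile 5.2.2 with 3.4.2.1 and Tables 5 and 6. Replace the Day 1 to Day 87 period with one tied to each dose and identical in all groups: from the day of each vaccination through 30 days after it, or until the device is collected if that is earlier. Nominally this gives Days 1 to 31 for everyone and Days 61 to 91 for naive subjects, which are the protocol's own unsolicited-AE windows. The end should be the 30-day AE window and not the 30-day visit itself, because that visit may fall 7 days early or 10 days late. State whether the solicited-AE resolution clause extends or shortens the period.

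The cost is one sentence and one eDiary setting, with no extra visit. There are two small limits. An early visit still cuts the prompts short (a Day 24 visit leaves 24 of 31 days). Medically attended AEs after the 30-day period would have no eDiary prompt, but they remain covered by the scheduled calls and visits through Day 181 or Day 241.
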